6.11.3. Clinical Evaluation Tools

A. Parent/LAR reported Symptom Checklist

At the beginning of the study, parents/LARs will be provided with blank ‘symptom checklist’ forms. The symptom checklist to be used by the parents/LARs has been appended (Appendix 3). When a symptom is observed in the participant during the intervention period, the parents will be required to fill the symptom checklist as trained by study staff. The severity/intensity of severity assessment of the symptoms e.g. sore throat, dry cough, wet cough, runny nose, stuffy/blocked nose and sneezing will be made by parents/LARs as per the following criteria:

- Mild – Easily tolerated, causing minimal discomfort and not interfering with normal everyday activities.
- Moderate – Sufficiently discomforting to interfere with normal everyday activities.
- Severe – Any event that prevents normal everyday activities.

Parents/LARs will be trained by study staff to assess the symptoms based on above criteria. For the assessment of other symptoms e.g. diarrhea/loose stools, vomiting and fever, the criteria are already mentioned in the symptom checklist which are in

	Document Name	Clinical Study Protocol 204477		
	Type	Version	Document Identifier	Effective Date
	eldo_clinical_doc	5.0; Most-Recent; Effective; CURRENT	090032d580daa95e	10-Oct-2017 06:16:49
	Reason For Issue	Auto Issue		

line with assessment done as per CTCAE 2010. Parents/LARs will also be provided with digital thermometers to check temperature in case if fever is observed.

In cases where parents/LARs do not observe any symptoms in the participant, they will be asked to mark the relevant ('No') box mentioned for each symptom for each day in the symptom checklist. The symptom checklist will be handed to study physician on weekly basis for review by physician. The physician will then evaluate the symptoms, if any, to determine diagnosis.

Those requiring hospitalisation or specialised care will be referred to the secondary or tertiary care hospital, as deemed necessary by the study physician. The determined diagnosis will be captured in the CRF, and the severity will be graded based on the criterion indicated in Appendix 5.

B. Diagnosis Form

Diagnosis form (DF) will be used to note the diagnosis, severity and school absenteeism due to GI and respiratory illnesses only, as defined in the study protocol. DF will also be used to capture start and end date of all occurrences of GI and respiratory illnesses in the week.

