6.12. Study Physician Weekly Review

To ensure that no case is missed, a weekly review (SPWR) will be scheduled by the study physician to check symptom checklist from all participants.

 GlaxoSmithKline	Document Name	Clinical Study Protocol 204477		
	Type	Version	Document Identifier	Effective Date
	eldo_clinical_doc	5.0; Most-Recent; Effective; CURRENT	090032d580daa95e	10-Oct-2017 06:16:49
	Reason For Issue	Auto Issue		

SPWR will initiate 1 week (+up to 2 days) post first dietary counselling visit of the participant and will continue on a weekly basis (+ up to 2 days) until end of study visit. ~~At least one weekly review with the study physician will occur after product administration stops~~ **LAST SPWR WILL BE CONDUCTED ON END OF STUDY VISIT DAY, EVEN IF SYMPTOMS ARE ASSESSED FOR LESS THAN A WEEK IN SYMPTOM CHECKLIST FORM.**

In case the SPWR of a participant is not conducted due to reasons such as absenteeism, long holidays etc for a week, then every attempt will be made to contact and collect symptom checklist from participant/parents/LARs, either telephonically or visiting them at home. If any participant is not accessible for consecutive 4 weeks, he/she will be considered as lost to follow up.

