9.3.3. Secondary Analyses

Following secondary efficacy variables will be analysed for both completers (those who completed entire 9 months of study) and ITT population.

The secondary efficacy variables are:

- Frequency of GI and respiratory illnesses defined as total number of illness episodes of GI and/or respiratory illnesses, divided by duration of intervention, where each episode is defined as each incidence of illness followed by at least 3 symptom free days (Section 6.11.2).

The same model outlined above for primary outcome variable will be used for this secondary outcome.

- Severity of GI and respiratory illnesses (Mild, moderate, or severe intensity as captured in DF) (See Section 6.11.2 for details on capturing severity of illness).

This will be captured by study physician as per severity grading outlined in Appendix 5. Frequencies of intensity (Mild, moderate, or severe) by treatment groups will be compared using chi-square test (if frequencies are greater than 5%). If frequencies are $\leq 5\%$ in any treatment groups, then these will be compared using Fisher's exact test between treatment groups.

- School absenteeism due to GI and respiratory illnesses as identified from DF.

The same model outlined above for primary outcome variable will be used for this secondary outcome.

- Change from baseline (measured at screening visit) in BMI.

This will be analysed using an analysis of covariance (ANCOVA) model. The model will include the fixed factors for treatment, cluster (school) and gender; baseline BMI assessment recorded at screening visit as covariate.

- Change from baseline in gut integrity/health as measured by Lactulose:Mannitol test and Urinary Neopterin test defined in Section 6.9.1.1 respectively.

 GlaxoSmithKline	Document Name	Clinical Study Protocol 204477		
	Type	Version	Document Identifier	Effective Date
	eldo_clinical_doc	5.0; Most-Recent; Effective; CURRENT	090032d580daa95e	10-Oct-2017 06:16:49
	Reason For Issue	Auto Issue		

These will be analysed using an ANCOVA model. The model will include the fixed factors for treatment, cluster (school) and gender; baseline gut integrity/health assessment at baseline as covariate.

- Change from baseline in salivary IgA as defined in Section 6.9.1.2.

This will be analysed using an ANCOVA model. The model will include the fixed factors for treatment, cluster (school), and gender; baseline salivary IgA assessment at baseline as covariate.

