4.1.3 Analysis Populations

Six analysis populations are defined.

| Population | Definition / Criteria | Analyses Evaluated |
|--------------------------|---|---|
| All Screened Subjects | 
 All participants who enter the study and sign the informed consent form. This population includes screen failures as well. | 
 Disposition, AE listing |
| Enrolled Population | 
 All participants who attended baseline visit will be considered in enrolled population. | 
 Protocol deviations, AE, efficacy, demographic characteristic, disposition and medical history listings |
| Safety | 
 Comprise of all participants who received at least one dose of study product (i.e. either only dietary counselling or both supplement and dietary counselling) during the study. This population will be based on the product to which the participant was planned to receive. | 
 Safety |
| Intent-To-Treat (ITT) | 
 All participants in the safety population with any post-treatment assessment (SPWR is considered as post-treatment assessment) will be included in Intent-to-treat (ITT) population. This population will be based on the product to which the participant was planned to receive. | 
 Efficacy |
| Modified Intent-To-Treat | 
 All participants in the ITT population who have completed entire study of 9 months | 
 Primary, Secondary |

| Population | Definition / Criteria | Analyses Evaluated |
|--------------|--|--|
| (mITT) | 
(i.e., attended up to end study visit) will be included in modified intent-to-treat (mITT) population.
 
 This population will be based on the product to which the participant was planned to receive. | Exploratory Efficacy |

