4.4.2 Secondary Efficacy Variables

The analysis of secondary efficacy variables will be on the mITT population.

The secondary efficacy variables are:

- **Frequency of GI and Respiratory illness**

Frequency of GI and respiratory illnesses defined as total number of illness episodes of GI and/or respiratory illnesses, divided by duration of intervention in month, where each episode is defined as each incidence of illness followed by at least 3 symptom free days will be summarized in a table for the product groups (Table 14.2.3.1).

The frequency of GI and respiratory illnesses will be calculated as following –

Frequency (per month) = No of episodes X 30/ Number of days between first (BV) and last visit

Frequency of GI and respiratory illnesses will be analysed together using analysis of covariance (ANCOVA) model. The model will include cluster (school) as a random effect; fixed effects for product group and gender; and baseline IDDS as a covariate. Adjusted means, 95% confidence intervals, intraclass correlation, within product group p-values for each product group, product group difference, 95% confidence interval of the difference and the between-product group p-values based on the statistical model described above will also be presented (Table 14.2.3.2).

The assumptions of normality and homogeneity of variance will be investigated and violation of these assumptions may be overcome using suitable transformation or by performing sensitivity analysis or by appropriate non-parametric tests (e.g., Van Elteren, rank ANCOVA).

- **Analysis on Severity of GI and Respiratory illness:**

Frequency and percentages of severity episodes of GI and respiratory illnesses will be summarized in a table together and also separately (Table 14.2.4.1). If an episode comprises of occurrences of different severities, then the highest severity will be considered as the overall severity. Severity grades will be displayed in the tables for the GI and respiratory illness as mentioned in the Appendix 5 of the Protocol version 5.0.

Frequencies of severity (Mild, moderate, or severe) episode between product groups will be compared using Chi-Square test (if frequencies are greater than 5%). If frequencies are $\leq 5\%$ in any product group, then these will be compared using Fisher's exact test between product groups (Table 14.2.4.1).

- **Analysis of School absenteeism due to GI and Respiratory illness:**

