4.8 Analysis of Other Variables

Not applicable.

5 Changes to the Protocol Defined Statistical Analysis Plan

Any changes from the originally planned statistical analysis specified in the protocol (Dated: 10 October 2017) are outlined in Table 1.

Table 1 Changes to Protocol Defined Analysis Plan

| Protocol | Reporting & Analysis Plan |
|----------|---------------------------|
|----------|---------------------------|

| Statistical Analysis section | Statistical Analysis Plan | Rationale for Changes |
|---|--|---|
| 
 4.1.3 | 
 Enrolled population defined Modified ITT population defined | 
 Since this study uses cluster randomization and not individual participant's randomized so randomized population cannot be defined. Instead enrolled population defined. To allow the exclusion of some enrolled participants in a justified way (such as participant who were deemed ineligible after enrolment or certain participants who never started treatment). |
| 
 4.4.1 and 4.4.2 | 
 Primary, secondary and exploratory analysis will be done on mITT population. | 
 Primary analysis should be done on participants those who are presented entire study duration. Secondary and exploratory outcome data (particularly those involving analysis on human biological samples), are available only after End of study visit (visit 10). ANOVA model for analysis of ferritin, serum-transferrin receptor (sTfR), is modified. |
| 
 9.2.1 | 
 PP analysis will be performed in case there is a 5% difference observed between number of subjects in mITT (instead of ITT) and PP. | 
 This change has been incorporated since mITT is primary population of analysis |

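### SAP 4.4.2 drops the protocol's ITT analysis of episode frequency, severity and school absenteeism, for a reason that fits only the end-of-study measures

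*SAP*

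**What the plan says.** Protocol 9.3.3 opens its list of secondary variables with: "Following secondary efficacy variables will be analysed for both completers (those who completed entire 9 months of study) and ITT population". SAP 4.4.2 replaces this with one population: "The analysis of secondary efficacy variables will be on the mITT population". SAP 4.1.3 defines mITT as "All participants in the ITT population who have completed entire study of 9 months", that is, children who attended through the end visit. SAP 4.4.3 confirms that it holds completers only, with no imputation.

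SAP Section 5, Table 1 discloses the change and gives this reason for the secondary outcomes: "Secondary and exploratory outcome data (particularly those involving analysis on human biological samples), are available only after End of study visit (visit 10".

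The illness endpoints come from a different source. Protocol 6.11.3 states: "Diagnosis form (DF) will be used to note the diagnosis, severity and school absenteeism due to GI and respiratory illnesses only", and "DF will also be used to capture start and end date of all occurrences of GI and respiratory illnesses in the week". Protocol 6.12 sets the timing: "SPWR will initiate 1 week (+up to 2 days) post first dietary counselling visit of the participant and will continue on a weekly basis". SAP 4.4.2 then computes episode frequency over each child's own follow-up: "Frequency (per month) = No of episodes X 30/ Number of days between first (BV) and last visit".

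**The concern.** The stated reason concerns when data become available, and it is applied to all secondary outcomes alike. Three of them do not wait for Visit 10. A child who withdraws in month 5 already has weekly records of episodes, severity and missed school days. Under the SAP these records are listed but not analysed.

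Leaving the study happens after allocation, in an open-label trial, and may be related to illness or to the burden of a twice-daily drink. A comparison of completers can then differ from a comparison of all children followed. For these endpoints the protocol's paired analysis (completers and ITT) was the planned way to see whether it does. The SAP removes half of that pair and leaves usable child-time out.

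**Working it through.** **Which reason fits which endpoint**

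- Blood, urine and saliva measures, BMI, dietary diversity and dietary recall: measured at screening or baseline and again at Visit 10 (Protocol, Schedule of Events). A child who leaves early has no end value, so the Table 1 reason holds.
- Episode frequency: built from occurrence dates on the weekly form (Protocol 6.11.3, Appendix 5). The reason does not hold.
- Severity: graded on the same weekly form. The reason does not hold.
- School absenteeism: days entered per week on the same form. The reason does not hold.

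**What ITT analysis is left**

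- SAP 4.4.1.3: MMRM in ITT, primary endpoint (ill days) only.
- SAP 4.6: ITT analyses of ill days at 3 and 6 months, and of GI and respiratory ill days separately at 3, 6 and 9 months.
- SAP 4.6 also covers frequency, severity and absenteeism, but only by gender at nine months and with no ITT version named.
- SAP 4.1.3: the per-protocol analysis is limited to the primary variable. ITT is labelled for efficacy in general, but no model or table is given for the three endpoints.

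None of these gives an ITT analysis of frequency, severity or absenteeism.

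**The plan's own numbers (Protocol 9.1, SAP 1.4)**

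- Pooled SD = sqrt((2.65² + 2.51²)/2) = 2.581. A difference of 0.7 at two-sided 0.05 and 80% power gives 214 per arm by the normal approximation and 214.4 by the t-test, so 215.
- 215 × 1.5 = 322.5, so 323 per arm and 646 in total.
- 323/0.7 = 461.4, so 462 per arm and 924 in total. The stated figures reproduce.

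**Children and child-time left out**

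- 924 − 646 = 278, and 278/924 = 30.1%. This is an upper bound: ITT requires study product and at least one post-treatment assessment, so some leavers would not enter ITT.
- The documents do not say when children leave. Assume a mean of 4.5 months, range 2 to 6.
- Completers' child-months: 646 × 9 = 5814.
- Leavers at 4.5 months: 278 × 4.5 = 1251; share = 1251/(1251 + 5814) = 1251/7065 = 17.7%.
- At 2 months: 556/6370 = 8.7%. At 6 months: 1668/7482 = 22.3%.

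**Illustration of a possible shift (assumptions, not a forecast)**

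Suppose leavers in one arm only had 1.5 times the completers' episode rate, with dropout equal between arms so that the share s above applies within each arm. The all-children rate in that arm is then 1 + 0.5s times its completer rate, and the completer rate falls short of it by 0.5s/(1 + 0.5s).

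- s = 0.177: 0.0885/1.0885 = 8.1%.
- s = 0.087: 0.0436/1.0436 = 4.2%.
- s = 0.223: 0.1115/1.1115 = 10.0%.

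If both arms had equal dropout and the same excess, both rates would be multiplied by the same factor and the rate ratio would not change.

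**The case against.** The best case for the SAP has four parts.

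- The change is open. Table 1 states the move to mITT, and its wording singles out biological samples. That stands, so a reader should not infer concealment, or that the reason is wrong throughout. It is too broad: SAP 4.4.2 makes no exception for the illness endpoints. Table 1's other ground for mITT, excluding ineligible or never-treated children, does not match a completer definition and would not justify removing treated children who leave.
- Illness in early leavers is not ignored. The ITT analyses of ill days use the same weekly forms and give a partial view of the effect of selecting completers. That also stands. They do not address episodes, severity or absenteeism. They do show that the SAP regards these weekly data as usable in ITT.
- ITT is not ready-made for all three endpoints. Frequency already has each child's own denominator. Absenteeism is a raw count of days (Protocol 6.11.2), so analysing it unadjusted in ITT would mix short follow-up with few missed days. This is correct, and the fix must deal with it.
- A count model is not what the protocol specified; it used the primary model for frequency and absenteeism. This is fair. A per-month rate weighted by days observed stays within the SAP's mixed linear model.

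**Conclusion.** The point holds as an analysis choice to correct. For three illness secondaries the SAP gives up an ITT analysis that the protocol required, for a reason that does not apply to them, and nothing else in the SAP replaces it. At the planning allowance this leaves out up to 278 of 924 children and, on the assumed leaving times, about 18% (9% to 22%) of child-months.

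A reader might infer that the completer analysis is biased by nearly the effect the trial was designed to detect. The documents do not support that. The 30% is an allowance, not an observed rate. The leaving times and the 1.5-fold rate have no source in the documents. Placing the excess in one arm is a choice, and equal excess in both arms leaves the rate ratio unchanged. The planned 10% difference belongs to total ill days, and Protocol 9.1 makes no sample-size provision for secondary objectives. The 8.1% (4.2% to 10.0%) is an illustration only. The case for acting rests on the lost protocol analysis and the ill-fitting reason. The primary analysis and the sample size are not affected by this point.

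**What to change.** - In SAP 4.4.2, restore the protocol's ITT analysis beside mITT for episode frequency, severity and school absenteeism. Keep mITT alone for biological samples, BMI and diet.
- In ITT, account for each child's follow-up in both frequency and absenteeism, either by a per-month rate weighted by days observed or by a count model with log(days observed) as offset. Keep school as the cluster and the same covariates. State what ends the observed period for a child who leaves early, for example the last weekly review.
- Tabulate severity per episode, including the episodes of early leavers.
- In SAP Section 5, Table 1, reword the reason so that it does not cover these three endpoints.

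Cost: SAP wording and about three extra tables. No new data and no additional children are needed.
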